At day 7, if live lice are still present, a repeat treatment will be administered. After day 7 if a subject reports clear signs of infestation (i.e., the presence of live lice), they will be regarded as a treatment failure and they will be offered treatment with an alternative product (viz., Vamousse Mousse) by clinical staff.

For the treatment group, Clinical staff will apply Vamousse Spray 'n' Go to fully coat dry hair and scalp, avoiding the eyes and mucus membranes. The Treatment will be left on the hair and scalp for 8 hours, then standard at home shampoo and rinsed off with warm water, followed by combing. The Treatment spray bottle is intended for a single use although it contains a sufficient quantity for two treatments. All household members will be instructed on an overall lice management program, which includes:

- Wash (in hot water) or dry-clean all recently worn clothing, hats, used bedding and towels.
- Wash (in hot water) personal care items such as combs, brushes and hair clips.
- Record time and date product shampoo/rinse 8 hours post treatment

For the control group, Clinical staff will first shampoo the hair and scalp using regular shampoo. They will then

thoroughly rinse and towel dry the hair and scalp, and allow hair to air dry for a few minutes. Shaking the permethrin lotion well before applying, they will proceed to thoroughly wet the hair and scalp with the permethrin lotion, being sure also to cover the areas behind the ears and on the back of the neck. After allowing the lotion to remain in place for 10 minutes, they will then rinse the hair and scalp thoroughly and dry with a clean towel.

The site will provide Subject with lice management instructions. Subjects will return for post-baseline visits assessments at Day 2, Day 7, and Day 14.

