4.2.2 Primary Endpoint

The proportions of participants in each of the study groups (i.e., treatment and control) who are completely free of live adult lice and nymphs at day 14

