4.2.3 Secondary Endpoints

- Assessment of infestations detected: number of live adult and nymph forms at the 7-day visit confirmed by investigator inspection during detection combing.
- Proportion of subjects requiring re-treatment at 7 days.
- Proportion lice free at day 2 (i.e., 24 hours after first treatment)
- Volume of product used in relation to hair type (Volume will be weighted pre and post and weight will be recorded on the product log. Hair type will be recorded as fine, medium or coarse on source document.)
- Safety of the product – as determined by reported adverse events during the study and recalled at the end of the treatment period.
- Cosmetic acceptability of the product in daily use as determined by consumer assessment questionnaire at the 14-day visit.
- The mean change between day 14 and baseline in the counts of live lice (i.e., total of live adult lice and nymphs) in each study group (i.e., treatment and control).

5. Study Enrollment and Withdrawal

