10.2 Data sets to be evaluated

The subject populations are defined as follows:

Safety Population includes all subjects who were administered treatment. This is the population that will be used for the safety assessments.

Modified Intent-to-Treat (mITT) population includes all subjects who met all inclusion/exclusion criteria, were randomized, administered treatment, and had at least one post-treatment efficacy evaluation. This is the primary population for determination of the effectiveness of the active treatment.

Per-Protocol (PP) population includes all mITT subjects who were administered treatment, had no protocol deviations which could have interfered with the accurate assessment of treatment efficacy, and returned for the Day 14 visit within the allowed window. This is the primary population for the efficacy comparisons between the two active treatment groups.

Subjects whose condition worsens and require alternate or supplemental therapy for the treatment of head lice during the study will be discontinued, included in both the mITT and PP population analyses as treatment failures. Subjects who discontinue early for reasons other than treatment failure will be excluded from the PP population, but included in the mITT population, using Last Observation Carried Forward (LOCF).

Efficacy analyses will be performed on both the per-protocol population and the mITT population. Safety analyses will be performed using the Safety population as defined.

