10.5 Sample Size

Sample size is 52. The requisite sample size for the *t*-test of the means of independent samples, assuming a Cohen's *d* of .40, alpha .05 two-tailed, and a power of .80, was smaller at 44. Thus, the larger requisite sample size for the *z*-test will also suffice for the *t*-test and will provide a cushion for the application of the Holm correction for Type I error. The sample size of 52 should be increased to account for a 10% expected dropout rate, resulting in a total sample size, rounded to an even number, of 58 (26 per group).

Expected difference:

40% difference between treatment groups, based on results of LiceFreee Spray (1% Sodium Chloride) compared to Permethrin; the results showed significantly higher pediculicidal activity for Sodium Chloride spray (85%) as compared to Permethrin (45%) at Day 15 ($p < 0.05$)¹.

A pilot study using Vamousse Spray 'n' Go as a once only treatment, showed high early lice kill (88% lice free at day 0 after treatment) but low efficacy at day 14 (12% lice free). It is anticipated that repeat dosing after 7 days, if live lice are present, will boost day 14 efficacy to levels similar to those at day 0.

Assumptions:

80% power, 0.05 alpha
Allocation ratio 1:1

Methods:

Calculations performed in Stata/IC 16.1
Binary data (lice free – Y/N) – proportions
Independent samples
Chi Squared, two-sided test

Sample:

Estimated sample sizes for a two-sample proportions test
Pearson's chi-squared test
 $H_0: p_2 = p_1$ versus $H_a: p_2 \neq p_1$
Study parameters:

```
alpha = 0.0500
power = 0.8000
delta = 0.4000 (difference)
p1 = 0.4500
p2 = 0.8500
```

Estimated sample sizes:

$N = 52$
 N per group = 26
Allowance for drop out: 10% per group, 3
Total sample: 29 per group (58)

References:

¹ Serrano, L. et al. Evaluation of the Efficacy and Safety of 1% Sodium Chloride (LiceFreee Spray) against 1% Permethrin Crème Rinse on Head Lice Infested Individuals. *Pharmacology & Pharmacy*, 2013, 4, 266-273.

11 Source documents and access to source data/documents

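### LOCF scores a subject who leaves after a lice-free Day 2 as cured at Day 14 in the mITT analysis, although the sponsor's single-application pilot shows early clearance does not last

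*Combined protocol and SAP*

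**What the plan says.** The primary endpoint (4.2.2) is the proportion in each group "who are completely free of live adult lice and nymphs at day 14". After baseline, "Subjects will return for post-baseline visits assessments at Day 2, Day 7, and Day 14" (4.1).

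Section 10.2 admits to mITT randomised, treated, eligible subjects who "had at least one post-treatment efficacy evaluation. This is the primary population for determination of the effectiveness of the active treatment". On early leavers it says: "Subjects who discontinue early for reasons other than treatment failure will be excluded from the PP population", while in the other set they are "included in the mITT population, using Last Observation Carried Forward (LOCF"). Subjects who worsen and need other lice therapy are counted as failures in both sets. No other missing-data method and no sensitivity analysis is described.

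Section 10.2 says of the per-protocol (PP) set: "This is the primary population for the efficacy comparisons between the two active treatment groups". The Synopsis (Statistical Analysis) instead makes mITT primary and PP secondary.

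Section 10.5 reports that the sponsor's pilot of the spray, used once only, "showed high early lice kill (88% lice free at day 0 after treatment) but low efficacy at day 14 (12% lice free"). It expects a repeat dose after 7 days, where live lice are present, to restore the Day 14 result. Section 4.2.3 describes the first follow-up reading as "Proportion lice free at day 2 (i.e., 24 hours after first treatment").

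**The concern.** LOCF is harmless only if lice status stays put after the subject leaves. For this product the plan itself reports the opposite: a high clearance rate straight after one application and a low one two weeks later. The Day 7 repeat treatment is there to deal with that fall. A subject who leaves between Day 2 and Day 7 has had one application and no repeat, so the single-application pilot is the most relevant evidence in the documents on what their Day 14 status would have been. LOCF ignores it and enters the Day 2 result as a Day 14 success.

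At stake is the spray's absolute Day 14 lice-free rate in mITT and, depending on what happens in the control arm, the comparison with permethrin.

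**Working it through.** **Inputs.** From 10.5: 29 per group, dropout allowance 3 per group, planned rates 0.45 (control) and 0.85 (spray), pilot rates 0.88 (day 0) and 0.12 (day 14), two-sided alpha 0.05. Assumed, because the documents do not give them: the spray's Day 2 lice-free rate (0.60 to 0.88), the control's early rate (0.45, 0.65 or 0.88), and that all dropouts leave after Day 2 and before Day 7.

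**The plan's own figure.** For 0.45 v 0.85 at 80% power:
- n = [1.96 × √(2 × 0.65 × 0.35) + 0.8416 × √(0.45 × 0.55 + 0.85 × 0.15)]² / 0.40² = 21.1, so 22 per group.
- With a continuity correction this becomes 25.9, so 26 per group and 52 in total, which matches 10.5.
- 26 / 0.90 = 28.9, so 29 per group and 58 in total, which also matches.

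**Size in the spray arm.** The overstatement is (dropouts / 29) × (rate carried forward − rate at Day 14 without repeat treatment).
- Day 2 rate 0.88: 3/29 × (0.88 − 0.12) = 0.079, or 7.9 points.
- Day 2 rate 0.60: 3/29 × (0.60 − 0.12) = 0.050, or 5.0 points.

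With completers at the planned 0.85 and a Day 2 rate of 0.88, LOCF gives (26 × 0.85 + 3 × 0.88)/29 = 85.3%. Using the pilot's Day 14 rate for the dropouts gives (26 × 0.85 + 3 × 0.12)/29 = 77.4%. Counting them as not lice free gives 26 × 0.85/29 = 76.2%.

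**Effect on the difference between arms.** With 3 dropouts per arm, completers at 0.85 and 0.45, and spray dropouts carried at 0.88, the LOCF difference by control early rate is:
- 0.45: 40.3 points
- 0.65: 38.2 points
- 0.88: 35.9 points

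Counting dropouts as failures in both arms gives 26 × 0.40/29 = 35.9 points.

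**Effect on false superiority.** I enumerated all binomial outcomes at 29 per arm and applied the pooled Z test of 10.1, counting only results significant in the spray's favour. Completers in both arms have a true rate of 0.45, and 3 spray dropouts are carried at 0.88.

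| Case | Z test |
|---|---|
| No dropouts | 2.4% |
| 3 per arm, control early rate 0.45 | 4.8% |
| 3 per arm, control early rate 0.65 | 3.3% |
| 3 per arm, control early rate 0.88 | 2.0% |

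Section 10.1 moves to an alternative such as Fisher's exact test when a group has fewer than 10 lice-free subjects. With Fisher's test in those cases the four figures become 1.7%, 3.8%, 2.7% and 1.7%.

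**Check on the remedy.** With completers at 0.45 and 3 dropouts per arm counted as failures, false superiority is 1.9%. With 0 spray and 6 control dropouts it is 9.3%.

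**The case against.** The strongest reply is that 10.2 names PP for the comparison between groups, and PP excludes these dropouts, so LOCF never touches that test. This stands as far as 10.2 goes. But the Synopsis makes mITT primary, 10.2 itself gives mITT the effectiveness claim, and both sets are to be analysed. How much the LOCF rule matters to the comparison depends on a conflict that the documents leave open.

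A second reply is that LOCF applies to both arms. This also stands. A reader might infer that the rule biases the superiority test towards the spray. The documents do not support that, because they give no early permethrin rate: with equal dropout and an equally high early rate in the control, the false-superiority rate is 2.0%, no worse than with no dropouts.

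A reader might also infer that three dropouts would overturn a positive result. For example, 21/29 v 13/29 gives p = 0.033, and removing 3 carried-forward spray successes gives 18/29 v 13/29, p = 0.19. That example corrects one arm only. If 3 control successes were carried forward too, the corrected result is 18/29 v 10/29, p = 0.036.

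Third, the pilot's 88% was measured on day 0, not Day 2, and came from a single application. Someone who leaves after Day 7 carries a Day 7 examination, with a repeat application if live lice were found, so the pilot's fall does not describe them. Both limits are accepted. They are why the size is given as a range and tied to departure before Day 7.

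Finally, LOCF does not turn every missing result into a success: a subject infested at the last visit is carried as not lice free.

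**Conclusion.** The concern holds for the spray's absolute Day 14 rate in mITT. The carry-forward assumption conflicts with the sponsor's own pilot for subjects who leave before the Day 7 re-treatment, and no other analysis tests it. The overstatement is about 5 to 8 points, if all 3 planned spray dropouts leave before Day 7, their Day 2 rate is 60% to 88%, and their untreated Day 14 rate is the pilot's 12%. Fewer early leavers shrink it in proportion.

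For the between-arm test the result is conditional: 4.8%, 3.3% or 2.0% false superiority for control early rates of 45%, 65% or 88%, against 2.4% with no dropouts. The documents do not show which applies, so a definite bias in favour of the spray should not be claimed. Whether mITT or PP carries the comparison is also unresolved between the Synopsis and 10.2.

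**What to change.** In 10.2, for the Day 14 lice-free endpoint in mITT, replace the LOCF sentence: a subject without a Day 14 lice examination counts as not lice free, in both arms and whatever the reason. Keep LOCF only as a labelled sensitivity analysis.

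Report dropouts by arm with last visit and last lice status. Section 10 already promises listings of all data, but a summary by arm is needed because failure imputation is itself biased when dropout differs between arms, as the 9.3% above shows, and the trial is open-label.

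Two passages have to be reconciled for the rule to work:
- State one Day 14 window. It is now ±3 days in the Synopsis (Study Duration) and 6.1.7, ±2 days in 7.3.4, and +2 days in 7.3.3.
- Say in both the Synopsis and 10.2 which population is primary for the comparison.

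The cost is a few sentences of text, with no change to visits or procedures. The downside is slightly lower lice-free rates in both arms. The rule does not reach dropouts with no post-treatment examination, who remain outside mITT.

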10.3 Statistical hypotheses

Primary Efficacy Endpoint:

Primary Outcome:

The proportion of subjects who are lice free (defined as no live lice, adults or nymphs) at day 14 will be greater in the treatment group than in the control group.

Secondary Outcome:

The mean change between day 14 and baseline in the counts of live lice (i.e., total of live adult lice and nymphs) will be greater in the treatment group than in the control group.

Secondary Efficacy Endpoint:

Primary Outcome:

The proportion of subjects who are lice free (defined as no live lice, adults or nymphs) at day 7 will be greater in the treatment group than in the control group

Secondary Outcome:

The mean change between day 7 and baseline in the counts of live lice (i.e., total of live adult lice and nymphs) will be greater in the treatment group than in the control group.

10.4 Description of statistical methods

10.4.1 Subject disposition and demography

Descriptive statistics will be generated by all subjects for selected continuous variables. The number and percentage of subjects in each class of categorical demographic and Baseline variables (e.g., gender, ethnicity, and race) will be tabulated by treatment group. Individual subject demographic and Baseline characteristic data will be listed

10.4.2 Assessment of primary and secondary endpoints

Primary Outcome:

To test the hypotheses for this outcome for each of the two endpoints, the counts of subjects in the treatment and control groups who were lice free at each endpoint will be converted into proportions of the respective group. These proportions along with the group sample sizes will be used to compute the necessary Z statistics for independent proportions.

Secondary Outcome:

To test the hypotheses for this outcome for each of the two endpoints, the difference between the day 14 and baseline counts of live lice (i.e., total of live adult lice and nymphs) will be computed for each participant. The mean difference in counts for the treatment and control groups will be tested using the t-test for independent means.

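### Section 10.4.2 specifies the Day 14 change in live-lice count for both endpoints, so the Day 7 count hypothesis in 10.3 has no matching test

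*Combined protocol and SAP*

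**What the plan says.** Section 10.3 sets two efficacy endpoints. Each has a lice-free proportion (called the primary outcome) and a change in count (called the secondary outcome).

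- Primary efficacy endpoint, count: "The mean change between day 14 and baseline in the counts of live lice" is expected to be greater with the test product.
- Secondary efficacy endpoint, count: "The mean change between day 7 and baseline in the counts of live lice" is expected to be greater with the test product.
- The lice-free hypothesis for the secondary endpoint is also at Day 7: "defined as no live lice, adults or nymphs) at day 7 will be greater in the treatment group than in the control group".

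Section 10.4.2 gives the methods. For the lice-free outcome it uses the subjects "who were lice free at each endpoint will be converted into proportions of the respective group", so each endpoint keeps its own visit. For the count outcome it specifies, "for each of the two endpoints, the difference between the day 14 and baseline counts of live lice", and then: "The mean difference in counts for the treatment and control groups will be tested using the t-test for independent means".

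Day 7 counts are collected. Section 4.1 describes the count at that visit, and 4.2.3 lists as a secondary endpoint the "number of live adult and nymph forms at the 7-day visit confirmed by investigator inspection during detection combing".

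**The concern.** The hypothesis section and the methods section disagree on which visit supplies the count for the secondary efficacy endpoint. An analyst who follows 10.4.2 word for word would never run a between-group test of the Day 7 change. The Day 14 test would be reported twice, once under a Day 7 label.

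The two visits are not interchangeable. Section 4.1 says: "At day 7, if live lice are still present, a repeat treatment will be administered". Day 7 is therefore the last count before any second application, while the Day 14 count reflects whatever that application did. At stake is whether a stated hypothesis about the first application is tested with the data that bear on it.

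**Working it through.** No figure in the plan bears on this point. The check is a comparison of the two sections, with a little algebra.

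**1. Hypotheses against methods**

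| Endpoint in 10.3 | Outcome | Visit in 10.3 | Visit in 10.4.2 | Match |
|---|---|---|---|---|
| Primary | Lice-free proportion | Day 14 | the endpoint's own visit | yes |
| Primary | Change in count | Day 14 | Day 14 | yes |
| Secondary | Lice-free proportion | Day 7 | the endpoint's own visit | yes |
| Secondary | Change in count | Day 7 | Day 14 | **no** |

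Two endpoints times two outcomes gives 2 × 2 = 4 hypotheses, and one of them is mismatched. No other section specifies a difference between Day 7 and baseline.

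**2. What literal execution returns**

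For subject *i*, let *B* be the baseline count, *C7* the Day 7 count and *C14* the Day 14 count. The declines are

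- D7 = B − C7
- D14 = B − C14

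Section 10.4.2 uses D14 for both endpoints. In the same population, with the same handling of missing values, the two t-tests have identical inputs. They therefore give the same t statistic and the same p-value.

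**3. Whether D14 could stand in for D7**

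Subtracting, D14 − D7 = C7 − C14, which is the fall in count between Day 7 and Day 14. The between-group difference in mean D14 equals that in mean D7 only if the two groups have the same mean fall over that interval.

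Nothing in the design makes that likely. Under 4.1, re-treatment depends on the Day 7 finding, and 4.2.3 makes the proportion needing re-treatment an endpoint in its own right, so the plan allows for the groups to differ on it. Section 10.5 also relies on re-treatment to move the Day 14 result. The pilot of a single application had 88% lice free on Day 0 after treatment and 12% at Day 14, and repeat dosing is expected to bring Day 14 back to about the Day 0 level.

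**4. Direction of the difference**

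Section 10.4.2 does not fix the order of subtraction. Section 4.2.1 describes the outcome as a decline from baseline, so a greater change in 10.3 means a larger fall. Section 10.5 plans the t-test as two-tailed, and reversing the subtraction changes neither |t| nor p. This is a matter of clear reporting only.

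**The case against.** The strongest reply is that this is a slip whose intent is plain. The sentence in 10.4.2 opens by saying that it tests the hypotheses for this outcome, 10.3 is explicit about Day 7, and the neighbouring paragraph on proportions uses each endpoint's own visit. A sensible analyst would use the Day 7 count. That reading is probably right, but it asks the analyst to override the methods text, and the choice of visit should not be left until data are in hand.

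A second reply is that 10.4.2 may be the correct side. Section 4.2.3 lists a mean change in count only for Day 14; for Day 7 it lists a number of lice, not a change. The synopsis names Day 2 as the secondary efficacy endpoint. So the Day 7 change hypothesis appears only in 10.3. This stands as a caution about the fix: the secondary time point is unsettled. It does not rescue 10.4.2, because a Day 14 difference applied to two endpoints is one test performed twice, whether the second endpoint is Day 2 or Day 7.

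Three stronger readings are tempting, and the documents do not support them.

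- *The Day 7 counts would go unanalysed.* They are a listed endpoint in 4.2.3. The opening of section 10 promises descriptive summaries, confidence intervals for secondary efficacy endpoints and full listings. The Day 7 lice-free proportion is tested. Only the between-group test of the Day 7 change is missing.
- *The duplicate wastes a step in the Holm procedure.* A Day 7 count hypothesis would take its place in the family whether computed correctly or not. Section 10.5 mentions Holm without saying which hypotheses the family contains.
- *The sign convention could reverse the conclusion.* It could not, given the decline wording in 4.2.1 and the two-tailed test.

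**Conclusion.** The point holds as an internal inconsistency. As written, 10.4.2 gives the wrong test for one stated hypothesis, the between-group difference in change from baseline to Day 7. Followed literally, that test duplicates the Day 14 test exactly, and its data carry the effect of any Day 7 re-treatment.

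The reach is limited. The primary endpoint (lice free at Day 14), its test and its sample size are unaffected, and the Day 7 data remain available and described. The text should be corrected before analysis, but the slip does not threaten the trial's main conclusion.

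The exact duplication assumes that both tests use the same population and the same handling of missing values. The statement about re-treatment assumes that subjects with live lice at Day 7 are re-treated, as 4.1 and 7.3.3 say. Section 5.5.1 instead ends participation for a subject found still infested on a revisit. Those sections contradict each other and must be reconciled. Whichever way that is done, 10.3 and 10.4.2 still name different visits.

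**What to change.** Replace the count sentence in 10.4.2 with wording to this effect: *for each endpoint, the decline is the baseline count minus the count at that endpoint's own visit: Day 14 for the primary endpoint, Day 7 for the secondary endpoint in 10.3.* Fixing the order of subtraction as a decline also brings the section into line with 4.2.1.

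In the same edit, settle the secondary efficacy time point across the synopsis (Day 2), 4.2.3 (Day 2 for the proportion, Day 7 for the count, Day 14 for the mean change) and 10.3 (Day 7). If the sponsor chooses a time point other than Day 7, 10.3 must change along with 10.4.2.

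The cost is one sentence in 10.4.2 plus aligned wording in the sections named. Section 4.1 already has lice counted at Days 0, 2, 7 and 14, so no visit, measurement or subject is added.

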7.3 Study schedule

7.3.1 Screening/randomization

Screening Visit Day 0 (Visit 1)

- Obtain informed consent of potential participant verified by signature on written informed consent.
- Record demographic information, obtain medical history, and history of head lice.
- Review medications history and concomitant/prohibited medications to determine eligibility
- Verify inclusion/exclusion criteria.
- Collect urine sample for pregnancy testing for all subjects of childbearing potential.
- Perform assessment for living head lice on subjects and household members for a minimum of 15 minutes. Each subject must have at least 1 live louse. Rate severity of infestation. After each subject has been identified, additional infested household members will also be assessed for infestation.
- Level of infestation will be rated as heavy, moderate or light described by how quickly lice were found during combing: heavy infestation = >1 louse with one stroke of the comb; moderate infestation = 1 louse with one stroke of the comb; light infestation = first louse found only after several strokes of the comb
- Household members must have an active head lice infestation defined as: At least 1 live lice (adult and/or nymph) present on the scalp and/or hair, as determined by a trained evaluator. Household members will be assigned to the same study group as index case.
- Schedule study visits for participants who are eligible and available for the duration of the study.
- Randomly assign subjects to treatment or control group based on infestation severity alternation system (i.e., randomly assign pairs of equal severity levels to treatment and control groups, a form of stratified random sampling) to achieve balanced representation of severity in the two groups.
- Investigational Product Dispensation/ Application for subject.
- Provide each subject with homecare instructions including combing after first wash out.
- Inform subject when to come back for each follow-up visit.
- Provide Standard of Care treatment on-site to unqualified infested household members.

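### Section 10.4.2 tests raw change in louse count with an unadjusted t-test, which is inefficient because most subjects' change is simply their baseline count

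*Combined protocol and SAP*

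**What the plan says.** Section 10.3 states the count hypothesis as "The mean change between day 14 and baseline in the counts of live lice" being greater in the treatment group, and pairs it with a Day 7 version. Section 4.2.3 lists the Day 14 mean change as a secondary endpoint.

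For the analysis, section 10.4.2 says "the difference between the day 14 and baseline counts of live lice (i.e., total of live adult lice and nymphs) will be computed" subject by subject, and then "The mean difference in counts for the treatment and control groups will be tested using the t-test for independent means". Sections 10, 10.1, 10.3 and 10.4 name no baseline covariate, severity term, transformation, percent change or count model.

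On burden at entry, section 7.3.1 requires only that "Each subject must have at least 1 live louse", and no upper limit is given. Section 4.1 has live lice counted at Day 0 and infestation rated heavy, moderate or light. Sections 4.1 and 7.3.1 use that rating to split subjects of equal severity between the arms.

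Section 10.5 addresses the power of this t-test: the requirement at a "Cohen's *d* of .40, alpha .05 two-tailed, and a power of .80, was smaller at 44", so that "the larger requisite sample size for the *z*-test will also suffice for the *t*-test".

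**The concern.** If a subject is lice-free at Day 14, the change score contains no information about the product beyond the fact of clearance. Its size is the number of lice that the subject started with. Two cleared heads, one with 2 lice and one with 40, score -2 and -40 although the product did the same for both. When most subjects clear, the spread of the change scores is largely the spread of the baseline counts. The unadjusted t-test carries all of that spread as noise.

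At stake is a formal secondary hypothesis. A product that performs as planned could show a clear difference in lice-free proportion and no significant difference in mean count change. That would look like a conflict between endpoints when it only reflects the choice of test.

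**Working it through.** **1. The plan's own figure.** For an independent t-test with d = 0.40, two-sided alpha 0.05 and 80% power, the normal formula gives

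n per group = 2(1.960 + 0.842)² / 0.40² = 2 × 7.85 / 0.16 = 98.1, so 99 (100 by the exact t).

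That is about 200 in total, so the 44 in section 10.5 does not reproduce. At d = 0.40 the exact power is 29% with 26 per group and 32% with 29 per group. This is a separate sample-size error. Its only bearing here is that 10.5 cannot be cited as evidence that the t-test is adequately powered. Nor does 10.5 tie d = 0.40 to the planned 85% v 45%, so power is derived from those rates below.

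**2. Inputs.** From section 10.5: lice-free 0.85 (test) and 0.45 (control), 26 per group, "Allocation ratio 1:1". The 29 per group is 26 plus the stated allowance ("Allowance for drop out: 10% per group, 3"). Assumed, because the documents give no mean, SD or distribution of counts: the coefficient of variation (CV) of the baseline count, and the fraction r of baseline that remains in subjects who are not cleared.

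**3. Structure of the outcome.** Let B be the baseline count and U = 1 if the subject is not cleared. The reduction is B(1 - rU). For cleared subjects it equals B. With equal arms, the cleared share is (0.85 + 0.45)/2 = 0.65.

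**4. Closed form.** In units of mean baseline, with q the probability of not clearing:

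- difference in mean reduction = (0.85 - 0.45) × r = 0.40r
- variance in an arm: v(q) = (1 + CV²)[(1 - q) + q(1 - r)²] - (1 - rq)²
- d = 0.40r / √{[v(0.15) + v(0.55)]/2}

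Example with CV = 1 and r = 0.5:

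- v(0.15) = 2(0.85 + 0.15 × 0.25) - 0.925² = 1.775 - 0.856 = 0.919
- v(0.55) = 2(0.45 + 0.55 × 0.25) - 0.725² = 1.175 - 0.526 = 0.649
- d = 0.20 / √0.784 = 0.23, which gives power 0.13

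Power of the raw-change t-test, 26 per group:

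| Baseline CV | r = 25% | r = 50% | r = 100% | r = 150% |
|---|---|---|---|---|
| 0.3 | 0.22 | 0.56 | 0.81 | 0.86 |
| 0.5 | 0.12 | 0.31 | 0.67 | 0.78 |
| 1.0 | 0.07 | 0.13 | 0.34 | 0.50 |
| 1.5 | 0.06 | 0.08 | 0.20 | 0.31 |

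Power nears or passes 80% only when baseline counts are fairly uniform and uncleared subjects keep or gain lice.

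**5. Comparison of analyses by simulation.** 26 per group, 85% v 45%, log-normal baseline with median 5-10 and log SD 0.5-1.2, and uncleared subjects at 30-150% of baseline (24 scenarios). For reference, CV = √(exp(SD²) - 1), so these log SDs correspond to CVs of about 0.53 to 1.8.

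| Analysis | Power over the scenarios |
|---|---|
| t-test on raw change (as planned) | about 5-73% |
| ANCOVA of raw count on baseline | about 47-77% |
| ANCOVA of log(count+1) on log(baseline+1) | about 76-87% |

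The t-test was the weakest of the three in all 24 scenarios, with or without severity pairing.

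**6. Bias or noise?** With no true difference, the t-test rejected in 4-5% of simulated trials. The fault is therefore imprecision.

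**7. Does severity-paired allocation rescue it?** Three simulated severity strata cut the share of trials whose point estimate favours the wrong arm, for example from 13-14% to 7-8% at log SD 0.8 and residual 60%. Power did not recover. At CV 1.0 and residual 50% it was 0.065 with pairing and 0.147 without, because the unadjusted t-test does not credit the balance that pairing creates.

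**The case against.** **The size depends on assumptions.** This stands. Nothing in the documents fixes the skewness of baseline counts or the residual burden. Section 10.5 reports a pilot that fell from 88% lice-free just after treatment to 12% at Day 14 after a single application. Lice can return, so residuals near or above baseline are plausible, and they raise t-test power. A reader who looked only at wide baseline spread and low residuals might infer that the test would nearly always fail. The full range does not support that.

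**Allocation already balances severity.** In part this stands. Pairing reduces chance imbalance and wrong-direction estimates. But three levels based on comb strokes do not fix the count, and an analysis that ignores the pairing gains no power from it.

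**A reader might infer that the arm with heavier infestation wins whatever the product does.** The documents do not support this. Assignment is meant to balance severity, and the type I error stays near 0.05. Imbalance can mislead within one trial but does not favour either product. Wrong-direction results are almost always differences in sign only. Statistically significant ones occurred in at most 0.7% of simulated trials.

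**The log-scale alternative partly repeats the primary endpoint.** This stands. With 85% zeros in one arm, log(count+1) behaves largely as a lice-free v not-lice-free contrast, and much of its power comes from there. Raw-count ANCOVA keeps the planned quantity but gains less, and it does not reach 80% in the scenarios run.

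**Conclusion.** The planned test is inefficient for this outcome and leaves it exposed to chance baseline imbalance, although the covariates that would reduce both problems are recorded. That conclusion follows from the definition of the change score and the planned clearance rates.

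The size rests on the assumed baseline distribution and residual fraction: about 5-73% power for the t-test, against about 47-77% and about 76-87% for the two adjusted analyses. The ordering held in every scenario; the exact percentages should not be read as predictions. The simulated models adjusted for baseline count only, so any further effect of a severity term is not quantified.

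The documents do not support a claim of systematic bias, or of certain failure. Only a secondary outcome is affected. The comparison of lice-free proportions stands apart from this point.

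**What to change.** In section 10.4.2, replace the independent t-test on raw change with one of the following, stated for each visit at which 10.3 has a count hypothesis (10.4.2 now describes only the Day 14 difference):

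- **To keep the planned quantity:** ANCOVA of the visit count (or the change) on treatment, baseline count and severity level. Report the adjusted difference in mean change with a 95% CI.
- **For more power:** ANCOVA of log(count+1) on treatment, log(baseline+1) and severity level, reported as a ratio of geometric means of (count+1), not as a ratio of counts.
- **If a ratio of mean counts is wanted:** a negative binomial model with the same covariates.

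If a log or ratio analysis is chosen, reword the hypotheses in 10.3 and the endpoint in 4.2.3 to match, and keep raw mean change as a descriptive summary.

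The cost is wording in these sections. No extra subjects, visits or data are needed. The drawbacks are small: the log and ratio options put a secondary outcome on a relative scale, and the log-scale result overlaps in part with the lice-free primary endpoint.
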